#### 9.2.1 Time Period and Frequency for Collecting AE and SAE Information

The collection of nonserious AE information should begin at initiation of study treatment until 100 days after the last treatment, at the timepoints specified in the Schedule of Activities ([Section 2](#)).

Nonserious AE information should also be collected from the start of a placebo lead-in period or other observational period intended to establish a baseline status for the participants.

Sections 5.6.1 and 5.6.2 in the Investigator Brochure (IB) represent the Reference Safety Information to determine expectedness of serious adverse events for expedited reporting. Following the participant's written consent to participate in the study, all SAEs, whether related or not related to study drug, must be collected, including those thought to be associated with protocol-specified procedures.

All SAEs must be collected that occur during the screening period and within 100 days of discontinuation of dosing. For participants assigned to treatment and never treated with study drug, SAEs should be collected for 30 days from the date of treatment assignment. If applicable, SAEs must be collected that relate to any later protocol-specified procedure (e.g., a follow-up skin biopsy).

The investigator must report any SAE that occurs after these time periods and that is believed to be related to study drug or protocol-specified procedure.

- Medical occurrences that begin before the start of study treatment but after obtaining informed consent will be recorded on the appropriate section of the eCRF section.
- All SAEs will be recorded and reported to Sponsor or designee within 24 hours, as indicated in [Appendix 3](#).
- The investigator will submit any updated SAE data to the sponsor within 24 hours of this being available.

Investigators are not obligated to actively seek AEs or SAEs in former study participants. However, if the investigator learns of any SAE, including a death, at any time after a participant has been discharged from the study, and he/she considers the event reasonably related to the study treatment or study participation, the investigator must promptly notify the sponsor.

The method of evaluating, and assessing causality of AEs and SAEs and the procedures for completing and reporting/transmitting SAE reports are provided in [Appendix 3](#).

### **9.2.2 Method of Detecting AEs and SAEs**

Adverse events can be spontaneously reported or elicited during open-ended questioning, examination, or evaluation of a participant. (In order to prevent reporting bias, participants should not be questioned regarding the specific occurrence of one or more AEs.)

### **9.2.3 Follow-up of AEs and SAEs**

- Nonserious AEs should be followed to resolution or stabilization, or reported as SAEs if they become serious (see [Appendix 3](#)).
- Follow-up is also required for nonserious AEs that cause interruption or discontinuation of study treatment and for those present at the end of study treatment as appropriate.
- All identified nonserious AEs must be recorded and described on the nonserious AE page of the CRF (paper or electronic). Completion of supplemental CRFs may be requested for AEs and/or laboratory abnormalities that are reported/identified during the course of the study.

After the initial AE/SAE report, the investigator is required to proactively follow each participant at subsequent visits/contacts. All SAEs, and non-serious AEs of special interest (as defined in [Section 9.2](#) will be followed until resolution, until the condition stabilizes, until the event is otherwise explained, or until the participant is lost to follow-up (as defined in [Section 8.3](#)).

All SAEs will be followed until resolution, until the condition stabilizes, until the event is otherwise explained, or until the participant is lost to follow-up (as defined in [Section 8.3](#)).

Further information on follow-up procedures is given in [Appendix 3](#).

#### **9.2.4 Regulatory Reporting Requirements for SAEs**

- Prompt notification by the investigator to the Sponsor of SAEs is essential so that legal obligations and ethical responsibilities towards the safety of participants and the safety of a product under clinical investigation are met.
- An investigator who receives an investigator safety report describing SAEs or other specific safety information (e.g., summary or listing of SAEs) from the Sponsor will file it along with the Investigator's Brochure and will notify the IRB/IEC, if appropriate according to local requirements.

Sponsor or designee will be reporting adverse events to regulatory authorities and ethics committees according to local applicable laws including European Directive 2001/20/EC and FDA Code of Federal Regulations 21 CFR Parts 312 and 320. A SUSAR (Suspected, Unexpected Serious Adverse Reaction) is a subset of SAEs and will be reported to the appropriate regulatory authorities and investigators following local and global guidelines and requirements.

#### **9.2.5 Pregnancy**

If, following initiation of the study treatment, it is subsequently discovered that a participant is pregnant or may have been pregnant at the time of study exposure, including during at least 5 half-lives after product administration, the investigator must immediately notify the BMS Medical Monitor/designee of this event and complete and forward a Pregnancy Surveillance Form to BMS Designee within 24 hours of awareness of the event and in accordance with SAE reporting procedures described in [Appendix 3](#).

In most cases, the study treatment will be permanently discontinued in an appropriate manner (e.g., dose tapering if necessary for participant safety). Please call the BMS Medical Monitor within 24 hours of awareness of the pregnancy.

Protocol-required procedures for study discontinuation and follow-up must be performed on the participant.

Follow-up information regarding the course of the pregnancy, including perinatal and neonatal outcome and, where applicable, offspring information must be reported on the Pregnancy Surveillance Form.

Any pregnancy that occurs in a female partner of a male study participant should be reported to Sponsor or designee. In order for Sponsor or designee to collect any pregnancy surveillance information from the female partner, the female partner must sign an informed consent form for

disclosure of this information. Information on this pregnancy will be collected on the Pregnancy Surveillance Form.

### **9.2.6 Laboratory Test Result Abnormalities**

The following laboratory test result abnormalities should be captured on the nonserious AE CRF page or SAE Report Form electronic, as appropriate. Paper forms are only intended as a back-up option when the electronic system is not functioning.

- Any laboratory test result that is clinically significant or meets the definition of an SAE
- Any laboratory test result abnormality that required the participant to have study treatment discontinued or interrupted
- Any laboratory test result abnormality that required the participant to receive specific corrective therapy

It is expected that wherever possible, the clinical rather than laboratory term would be used by the reporting investigator (e.g., anemia versus low hemoglobin value).

### **9.2.7 Potential Drug Induced Liver Injury (DILI)**

Wherever possible, timely confirmation of initial liver-related laboratory abnormalities should occur prior to the reporting of a potential DILI event. All occurrences of potential DILIs, meeting the defined criteria, must be reported as SAEs (see [Section 9.2](#) and [Appendix 3](#) for reporting details).

Potential drug induced liver injury is defined as:

- 1) AT (ALT or AST) elevation > 3 times upper limit of normal (ULN)

AND

- 2) Total bilirubin > 2 times ULN, without initial findings of cholestasis (elevated serum alkaline phosphatase),

AND

- 3) No other immediately apparent possible causes of AT elevation and hyperbilirubinemia, including, but not limited to, viral hepatitis, pre-existing chronic or acute liver disease, or the administration of other drug(s) known to be hepatotoxic.

### **9.2.8 Other Safety Considerations**

Any significant worsening noted during interim or final physical examinations, electrocardiogram, x-ray filming, any other potential safety assessment required or not required by protocol should also be recorded as a nonserious or serious AE, as appropriate, and reported accordingly.

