**4. OBJECTIVES AND ENDPOINTS**

**Table 4.-1: Objectives and Endpoints**

Objectives	Endpoints

Primary
 
To establish the tolerability of the combination of nivolumab and daratumumab in participants with advanced or metastatic solid tumors.
	
Incidence of adverse events (AE), serious adverse events (SAE) and specific laboratory abnormalities (worst grade).

Secondary
 
 
• To evaluate the objective response rate (ORR) of nivolumab combined with daratumumab in participants with advanced or metastatic tumors in each cohort.
 
• To assess progression free survival (PFS) of nivolumab combined with daratumumab in participants with advanced or metastatic tumors in each cohort.
 
• To characterize the pharmacokinetics of nivolumab and daratumumab in participants with advanced or metastatic tumors.
 
• To characterize the immunogenicity of nivolumab and daratumumab in participants with advanced or metastatic tumors
 
	
 
• ORR, duration of response (DOR), best overall response (BOR) in each cohort, based on RECIST 1.1 criteria (Appendix 7).
 
• Median PFS in each cohort
 
• Pharmacokinetic parameters, influence of intrinsic and extrinsic covariates and potential exposure-response relationship will be characterized using integrated analyses.
 
• Immunogenicity of nivolumab and daratumumab will be assessed by ADA positivity
 

[REDACTED]
 
[REDACTED]
 
[REDACTED]
	
[REDACTED]

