**ADVERSE EVENTS**

Adverse Event Definition:
An Adverse Event (AE) is defined as any new untoward medical occurrence or worsening of a preexisting medical condition in a clinical investigation participant administered study drug and that does not necessarily have a causal relationship with this treatment.
An AE can therefore be any unfavorable and unintended sign (such as an abnormal laboratory finding), symptom, or disease temporally associated with the use of study drug, whether or not considered related to the study drug.

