## SERIOUS ADVERSE EVENTS

Serious Adverse Event (SAE) is defined as any untoward medical occurrence that, at any dose:

Results in death

Is life-threatening (defined as an event in which the participant was at risk of death at the time of the event; it does not refer to an event which hypothetically might have caused death if it were more severe)

Requires inpatient hospitalization or causes prolongation of existing hospitalization (see NOTE below)
 
NOTE:
 
The following hospitalizations are not considered SAEs in BMS clinical studies:
 
 
○ a visit to the emergency room or other hospital department < 24 hours, that does not result in admission (unless considered an important medical or life-threatening event)
 
○ elective surgery, planned prior to signing consent
 
○ admissions as per protocol for a planned medical/surgical procedure
 
○ routine health assessment requiring admission for baseline/trending of health status (e.g., routine colonoscopy)
 
○ medical/surgical admission other than to remedy ill health and planned prior to entry into the study. Appropriate documentation is required in these cases
 
○ admission encountered for another life circumstance that carries no bearing on health status and requires no medical/surgical intervention (e.g., lack of housing, economic inadequacy, caregiver respite, family circumstances, administrative reason)
 
○ admission for administration of anticancer therapy in the absence of any other SAEs (applies to oncology protocols)
 

Results in persistent or significant disability/incapacity

Is a congenital anomaly/birth defect

is an important medical event (defined as a medical event(s) that may not be immediately life-threatening or result in death or hospitalization but, based upon appropriate medical and scientific judgment, may jeopardize the participant or may require intervention [e.g., medical, surgical] to prevent one of the other serious outcomes listed in the definition above.) Examples of such events include, but are not limited to, intensive treatment in an emergency room or at home for allergic bronchospasm; blood dyscrasias or convulsions that do not result in hospitalization.) Potential drug induced liver injury (DILI) is also considered an important medical event. (See Section 9.2.7 for the definition of potential DILI.)

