Suspected transmission of an infectious agent (e.g., pathogenic or nonpathogenic) via the study treatment is an SAE.

Although pregnancy, overdose, cancer, and potential drug induced liver injury (DILI) are not always serious by regulatory definition, these events must be handled as SAEs. (See [Section 9.2.5](#) for reporting pregnancies).

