7.5.2 Serious Adverse Events

Serious adverse events will be summarized for all treated subjects:

- Overall summary of SAEs by worst CTC grade (any grade, grade 3-4, grade 5) presented by SOC/PT.
- The analysis will be conducted using the 30-day safety window.

A by-subject SAE listing will be provided for the “enrolled subjects” population.

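### The SAP's AE and SAE summaries have no split by causality, so the primary tolerability endpoint cannot separate toxicity from any disease-progression events that sites report

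*Protocol*

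**What the plan says.** **Definitions (Protocol).** The primary endpoint in Table 4.-1 is the incidence of AEs, SAEs and specified laboratory abnormalities by worst grade, with no limit by cause. Appendix 3 defines an AE as "any new untoward medical occurrence or worsening of a preexisting medical condition in a clinical investigation participant administered study drug", whether or not the drug caused it. An SAE includes any untoward occurrence that "Results in death" or needs inpatient admission, and the list of admissions that do not count says nothing about progression. Appendix 3 adds: "Although pregnancy, overdose, cancer, and potential drug induced liver injury (DILI) are not always serious by regulatory definition, these events must be handled as SAEs". Section 9.2.8 asks for AE or SAE recording, as appropriate, of "Any significant worsening noted during interim or final physical examinations, electrocardiogram, x-ray filming, any other potential safety assessment required or not required by protocol". In the AE rules of Section 9.2, tumor progression appears only as something to rule out before an event is called immune-mediated.

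**Analysis (Protocol).** Section 10.3.2 plans tables by worst grade of all AEs, treatment-related AEs, SAEs and treatment-related SAEs. Appendix 3 requires a physician's causality assessment for every AE.

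**Analysis (SAP).** Section 7.1.1 makes the default for AE tables on-treatment events of any cause, with each subject counted once in the overall total. Section 7.5.2 plans an "Overall summary of SAEs by worst CTC grade (any grade, grade 3-4, grade 5) presented by SOC/PT". Section 7.5.3 does the same for AEs leading to discontinuation, and 7.5.4 for all AEs. All three use the window of 30 days after last dose. None overrides the default on causality. Section 7.5.1 lists deaths by subject and does not summarize them.

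**The concern.** Progression is already measured as efficacy through PFS and best overall response. If it also enters the safety tables and no table separates it, the SAE, Grade 5 and AE-discontinuation totals mix harm from the combination with failure of the combination to work. A site that reports progression as an AE and one that does not would contribute different rates for the same clinical course.

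The design makes overlap in time likely. Scans run every 6 weeks for the first 24 weeks, treatment stops at confirmed progression, and it may continue past initial progression under Section 7.1.5. Progression events can therefore fall on treatment or within 30 days of last dose.

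The distinction has already mattered in this trial. SAP 2.1 says that no safety signal was validated because there was no pattern of severe events that underlying disease or prior therapy could not explain. The planned summary tables could not show a reader that separation.

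**Working it through.** **1. The plan's own safety figure.** Protocol 10.1 and SAP 5 say that 40 participants give more than 87% probability of detecting an event with 5% incidence. The check is 1 - 0.95^40 = 0.8715, which reproduces it. The figure takes no account of cause: a progression event with 5% incidence has the same 87% chance of appearing.

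**2. Can progression enter the tables?** Under Appendix 3, worsening of the study cancer is worsening of a preexisting condition, and death from it is an event that ends in death. No visible rule in Section 9.2 or Appendix 3 takes either out. Neither does any visible rule expressly order sites to report progression. So it is counted when a site reports it and the event falls in the window.

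**3. Does any summary table separate it?**

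| Summary | Protocol 10.3.2 | SAP 7.5 |
|---|---|---|
| All-cause AEs by worst grade | planned | planned (7.5.4) |
| All-cause SAEs by worst grade | planned | planned (7.5.2) |
| Treatment-related AEs | planned | absent |
| Treatment-related SAEs | planned | absent |
| AEs leading to discontinuation, by cause | not stated | absent (7.5.3 is all-cause) |
| Deaths by cause | not stated | absent (listing only, 7.5.1) |

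The exploratory look at hypersensitivity and infusion reactions in SAP 7.6 concerns antibody status and does not fill the gap.

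**4. Illustration of size.** The documents give no rate of progression SAEs in the window, so every rate here is assumed. Let d be the share of participants with a non-progression SAE and q the share with a progression SAE. If the two are independent, the tabulated share is 1 - (1 - d)(1 - q).

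| d | q | Tabulated share | Tabulated share minus q |
|---|---|---|---|
| 20% | 10% | 1 - 0.80 × 0.90 = 28% | 18% |
| 20% | 40% | 1 - 0.80 × 0.60 = 52% | 12% |
| 5% | 5% | 1 - 0.95 × 0.95 = 9.8% | 4.8% |
| 5% | 40% | 1 - 0.95 × 0.60 = 43.0% | 3.0% |

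The last column shows why subtracting the progression row does not return d: participants with both kinds of event are counted once in the total, so subtraction removes them altogether. Without independence, the tabulated share lies between the larger of d and q and their sum. With d = 20% that is 20-30% at q = 10%, and 40-60% at q = 40%.

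**5. The same in counts.** Suppose 8 of 40 have a non-progression SAE: 20.0% (95% CI 9.1-35.6). If 12 others have progression as their only SAE, the table shows 20 of 40: 50.0% (33.8-66.2). Both intervals are in Protocol Table 10.1-1.

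**The case against.** The strongest reply is that the endpoint is defined as the incidence of AEs and SAEs with no causality limit, so all-cause tables report exactly what was promised, and this is a close-out synoptic report. That stands as a defense of having all-cause tables. It does not explain dropping the treatment-related tables that the protocol itself plans.

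Several stronger readings are tempting, and the documents do not support them.

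- A reader might infer that Section 9.2.8 makes RECIST progression on a scan an AE. The section speaks of safety assessments and of recording as appropriate, while the schedule of activities and Section 9.1 class tumor imaging as efficacy. The point rests on Appendix 3 and SAP 7.1.1 instead.
- A reader might infer that the rule on cancer makes the disease under study an SAE. It stands beside pregnancy, overdose and liver injury, which arise on study, and it may mean new cancers only.
- A reader might infer that progression is certain to be counted as toxicity. The documents are silent, and the CRF completion guidelines and the Data Presentation Plan, which might settle it, are not among them.
- A reader might infer that the toxicity rate is lost altogether. The tables show preferred terms, and the SAP plans by-subject listings of deaths, SAEs, discontinuations and AEs. Someone holding the listings could recover much of it by hand; a reader of the summaries could not.
- A reader might infer that most stops for progression will appear as AE discontinuations. Section 8.1 gives progression as its own reason, and SAP 7.2.1 tabulates reasons separately. Only an AE whose recorded action is drug discontinuation enters 7.5.3.

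The 30-day window also keeps later deaths from progression out of the tables.

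**Conclusion.** The point holds in a limited form. The definitions as written let progression of the study cancer, and death from it, into the safety data, and no planned summary of the primary endpoint takes it out again. The firmest part needs no assumption: Protocol 10.3.2 plans treatment-related AE and SAE tables, causality is assessed for every AE, and the SAP omits those tables.

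The size cannot be derived from the documents. The 28-52% range depends on an assumed 20% non-progression SAE rate, an assumed 10-40% progression SAE rate within the window, and independence between them. If sites report little progression as AEs, the effect is small, but the planned summaries give no subject-level total from which to judge it. This is a question of interpreting the primary endpoint. It does not show that participants are at added risk or that the all-cause tables are wrong.

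**What to change.** Keep the all-cause tables and every AE and SAE reporting rule unchanged. In SAP 7.5.2 to 7.5.4:

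1. Restore the treatment-related AE and SAE tables by worst grade, as planned in Protocol 10.3.2.
2. Add subject-level totals, with Grade 3-4 and Grade 5 columns, that leave out events coded only as progression of the cancer under study. Fix the list of preferred terms by medical review before database lock, and keep in any event that the investigator calls drug-related.

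The two additions complement each other. The term list cannot remove clinical consequences of progression coded under other terms, while the treatment-related tables rest on investigator judgment in an open-label study.

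Do not rewrite Section 9.2.8 at this stage. Enrollment is closed, a new recording rule would make later data differ from earlier data, and it would conflict with leaving reporting unchanged.

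The cost is a few extra tables from data already collected, and medical review time to agree the list.

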## **9.3 Overdose**

An overdose is defined as the accidental or intentional administration of any dose of a product that is considered both excessive and medically important. All occurrences of overdose must be reported as an SAE (see [Section 9.2](#)).

## **9.4 Safety**

Planned time points for all safety assessments are listed in the Schedule of Activities ([Section 2](#)).

### **9.4.1 Physical Examinations**

Refer to Schedule of Activities: Section 2.

### **9.4.2 Vital signs**

Refer to Schedule of Activities: Section 2.

### **9.4.3 Electrocardiograms**

Refer to Schedule of Activities: Section 2.

### **9.4.4 Clinical Safety Laboratory Assessments**

- Investigators must document their review of each laboratory safety report.
- A local laboratory will perform the analyses and will provide reference ranges for these tests. Results of clinical laboratory tests performed on Day -1 must be available prior to dosing.
- Results of all laboratory tests required by this protocol must be provided to BMS, recorded either on the laboratory pages of the CRF or by another mechanism, as agreed upon between the investigator and BMS (eg, provided electronically). If the units of a test result differ from those printed on the CRF, the recorded laboratory values must specify the correct units. Any abnormal laboratory test result considered clinically significant by the investigator must be recorded on the appropriate AE page of the CRF.

The laboratory tests that will be performed for study participants are shown in [Table 9.4.4-1](#)

